Because the effects of the drug are not well studied in pregnancy and during breastfeeding, it is possible that there are harmful side effects that are not yet known to both the mother and unborn or breast-feeding child. Therefore, pregnant and breastfeeding subjects are excluded from the study. Additionally, the risks of this study includes risks of breach of confidentiality. While every effort will be made to protect the confidentiality of study subjects, there is a potential risk of an inadvertent or unintended breach of confidentiality.

As demonstrated in patients who have used 5% Imiquimod for other FDA approved indications, risks of topical application of 5% imiquimod are minimal. Additionally, previous studies as well as our preclinical data indicates that 5% imiquimod could modulate wound healing and prevent keloid recurrence in patients when applied prior to keloid-excision and continued after the procedure. Therefore, we believe that the benefit of possible decrease in keloid recurrence outweighs the minimal risks posed by topical 5% imiquimod therapy.

2 Study Objectives

Primary Objective

To assess the efficacy of 5% Imiquimod cream on preventing keloid recurrence after excision. Subjects will be evaluated by a consultant dermatologist at 2, 4, and 8 weeks following excision and by phone 12 weeks after excision to assess for clinical evidence of lesion recurrence.

[figure not shown]
Secondary Objectives

To assess the safety and tolerability of 5% Imiquimod in subjects undergoing keloid excision. Subjects will be evaluated by a consultant dermatologist at 2, 4, and 8 weeks following excision to assess for local site reaction such as redness, discomfort, swelling, and ulceration.

3 Study Design

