3.4 Primary Safety Endpoints

To assess the safety and tolerability of 5% Imiquimod in subjects undergoing keloid excision.

At each clinic follow-up visit (2, 4, 8 weeks after excision), the investigator will rate the local site reaction on the following scale:

- None
- Mild reaction (slight redness, discomfort, no swelling, no ulceration)
- Moderate reaction (redness, pain and swelling, no ulceration)
- Severe reaction (redness, pain, swelling, and ulceration)

4 Subject Selection and Withdrawal

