4.4.2 Data Collection and Follow-up for Withdrawn Subjects

Protected Health Information to be collected include names and medical record numbers. Additional information that is to be collected from patient's electronic medical record are:

- Race/ethnicity/gender
- And all elements of dates for dates that are directly related to the patient
- Current medications
- Symptoms related to treatment
- Physical examination
- Treatment and response
- Unidentifiable photodocumentation of lesions

Patients who choose to withdraw from the trial will be asked for permission for phone follow-up 12 weeks after excision date.

Patients who are withdrawn from the study for any reason but have initiated at least 1 imiquimod treatment will be seen in the outpatient clinic for one additional follow-up visit after their withdrawal date to observe the application site.

This information will be associated with a study ID. A master list with PHI and study IDs will be maintained by personal investigators in a secure location. Access will be given to only study personnel as needed. Data sets will only include assigned study IDs. Data will be backed up as a password protected file on a Penn Medicine secure server. Links to identifiers will be destroyed after the study is completed.

5 Study Drug

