5.9.4 Return or Destruction of Study Drug

At the completion of the study, subjects will be asked to return all unused medication at the final follow-up visit. There will be a final reconciliation of drug shipped, drug consumed, and drug remaining. This reconciliation will be logged on the drug reconciliation form, signed and dated. Any discrepancies noted will be investigated, resolved, and documented prior to return or destruction of unused study drug. Drug destroyed on site will be documented in the study files.

CONFIDENTIAL

6 Study Procedures

Patients will be recruited through the routine work of the Dermatology departments at the Hospital of the University of Pennsylvania. Recruitment and consent will be obtained by the principle investigator or another Dermatology physician as delegated by the investigator seeing the patient in the outpatient clinic. Patients seen in the outpatient clinic with clinical representation of keloids will be approached by the Dermatology attending as part of clinical evaluation, and written, informed consent will be obtained from the patient prior to any research related procedures are conducted.

It will be explained to the potential participant that entry into the trial is entirely voluntary and that their treatment and care will not be affected by their decision. It will also be explained that they can withdraw at any time. In the event of their withdrawal it will be explained that their data collected so far will be retained and used as part of the study analysis.

	Visit 1 (Week 1)	Visit 2 (Week 2)	Visit 3 (Week 4)	Visit 4 (Week 6)	Visit 5 (Week 10)	Phone encounter (Week 14)
Informed consent	X					
Urine pregnancy test	X					
Imiquimod application	X (start after visit)	X	X	X		
Keloid excision		X				
Excision specimen sent to pathology per SOC		X				
Photograph of lesion	X (optional)	X (optional)	X (optional)	X (optional)	X (optional)	
Evaluation of local site reaction		X	X	X	X	
Evaluation for recurrence			X	X	X	X

6.1 Visit 1

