Diagnosis of keloid will be made clinically by a Dermatology attending in the University of Pennsylvania Dermatology outpatient clinic. If the patient meets all inclusion and exclusion criteria set by the study and wishes for the keloid to be surgically removed, the patient will be approached by the Dermatology team for recruitment into the study. The patient will be given the opportunity to have a further discussion about the study and receive answers to any questions they may have. If the patient is agreeable to participating in the study, written and informed consent will be obtained from the patient or the patient's legally authorized representative. A medical history will be taken, demographic data will be collected, and photo-documentation of the lesions will be recorded.

A urine pregnancy test will be conducted prior to receiving study drug, for all female subjects of childbearing potential who are not postmenopausal > 1 year or surgically sterile. Subjects with a positive urine pregnancy test will be excluded from the study. Subjects will be asked to use contraception during treatment period. If

CONFIDENTIAL

indicated, (missed period, unprotected sexual intercourse, or Investigator discretion), a urine pregnancy test may be administered subsequently at the discretion of the Investigator.

A procedure appointment will be made for the surgical keloidectomy, and the subject will be instructed to apply Imiquimod 5% daily Monday to Friday the week prior to the scheduled excision date. The cream should be left in place for approximately 8 hours. The treatment area should include a 1 cm margin of skin around the tumor. The diameter of cream droplet applied should range from 5 mm to 10 mm for keloid areas of 0.5 cm to 5 cm, respectively.

The subject will also continue applying 5% Imiquimod daily as instructed for 5 more weeks after surgery. Subjects will be followed-up in the outpatient clinic at 2, 4, and 8 weeks post-excision and by phone 12 weeks post-excision.

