6.2 Visit 2 – Procedure visit

Consent for and surgical removal of keloid will be performed in accordance with current standard of care. Keloid excision sample will be sent to pathology per standard of care.

6.3 Visits 3 and 4

Scheduled clinic visits will be at 2 and 4 weeks after the surgical excision (weeks 3 and 5 after initiation of Imiquimod). At these visits, the following will be recorded:

- Subject compliance with therapy – if doses were missed
- The investigator will evaluate for evidence of keloid recurrence
- The investigator will rate the local site reaction on the following scale:
 - None
 - Mild reaction (slight redness, discomfort, no swelling, no ulceration)
 - Moderate reaction (redness, pain and swelling, no ulceration)
 - Severe reaction (redness, pain, swelling, and ulceration)
- The dose of Imiquimod will be adjusted to according to the following algorithm:
 - If intolerable at 5 days per week; stop completely for 1 week then restart but at a reduced dose of 3 days per week. Increase to 5 days per week as soon as tolerable.
 - If intolerable at 3 days per week, a further week off, start again at 3 days per week. Stop if intolerable.
- Any new medication usage and health service usage data will be recorded.

6.4 Visit 5

Last scheduled clinic visit will be at 8 weeks after surgical excision (3 weeks after completing Imiquimod therapy). The investigator will evaluate for evidence of keloid recurrence at this visit and evaluate for any local site reactions per above.

If treatment of the lesion with Imiquimod is stopped because of local toxicity, this will prompt an unscheduled clinic visit so that the dose adjustment algorithm can be implemented.

If at any point during the treatment phase, the keloid is judged to have recurred, then the subject will progress immediately to intralesional injection or re-excision in accordance with current standard of care.

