8.2 Recording of Adverse Events

At each contact with the subject, the investigator must seek information on adverse events by specific questioning and, as appropriate, by examination. Information on all adverse events should be recorded immediately in the source document, and also in the appropriate adverse event module of the case report form (CRF). All clearly related signs, symptoms, and abnormal diagnostic procedures results should be recorded in the source document, though should be grouped under one diagnosis.

All adverse events occurring during the study period must be recorded. The clinical course of each event should be followed until resolution, stabilization, or until it has been determined that the study treatment or participation is not the cause. Serious adverse events that are still ongoing at the end of the study period must be followed up to determine the final outcome. Any serious adverse event that occurs after the study period and is considered to be possibly related to the study treatment or study participation should be recorded and reported immediately.

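### Section 7.3 analyses only completers, against Sections 4.3 and 4.4.1, so patients who leave because of toxicity could vanish from the tolerability result

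*Combined protocol and SAP*

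**What the plan says.** **Analysis set.** Section 7.3 is one sentence. It puts subjects who completed the protocol into the analysis and names no separate safety population. Section 4.3 says that patients will be told their data up to withdrawal are kept and analysed. Section 4.4.1 repeats this and says it will appear in the information sheet and consent form.

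**Stopping and withdrawal.** Section 4.4.1 lists the reasons for stopping imiquimod early, and intolerable local or systemic toxicity is one of them. Only patients who withdraw consent are expressly taken out of the trial. Under Section 4.4.2, patients withdrawn for any reason who "have initiated at least 1 imiquimod treatment will be seen in the outpatient clinic for one additional follow-up visit after their withdrawal date", so that the application site can be observed. Section 7.1 allows for about 20% withdrawal among 10 patients.

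**Tolerability endpoint.** Tolerability is the secondary endpoint (Section 3.3) and safety and tolerability the primary safety endpoint (Section 3.4). Section 3.4 states: "At each clinic follow-up visit (2, 4, 8 weeks after excision), the investigator will rate the local site reaction on the following scale", with grades none, mild, moderate and severe. Section 2 gives the same times: "Subjects will be evaluated by a consultant dermatologist at 2, 4, and 8 weeks following excision to assess for local site reaction". Section 7.2 has endpoints other than response rate presented descriptively.

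**Visit 2.** The Section 6 schedule has a row "Evaluation of local site reaction", marked at Visit 2 (excision) as well as at 2, 4 and 8 weeks after excision. Section 6.2 covers surgical consent, excision and pathology ("Keloid excision sample will be sent to pathology per standard of care") and mentions no rating.

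**The concern.** A tolerability summary should include the patients who could not tolerate the drug. If the analysis set is defined by finishing the protocol, and toxicity is one route to not finishing, then membership of the set depends on the outcome being measured. Any resulting error favours the drug. Where a patient leaves because of toxicity, a completers' table would omit both the stop and any reaction grades recorded beforehand.

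The conflict also leaves the analyst a choice. With 10 patients, deciding after the data are seen whether one or two withdrawn patients count can change the reported result visibly. Patients, meanwhile, will have been told that their data are used.

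The Visit 2 mismatch is smaller. It touches the week of treatment before surgery, which Sections 1.4 and 1.5 present as what is new in this study, and no text says when at that visit, or on what scale, the site is rated.

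**Working it through.** **1. The statements side by side.**

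| Section | Withdrawn patients' data |
|---|---|
| 4.3 | Kept and analysed |
| 4.4.1 | Kept and analysed; patients are told so in the consent form |
| 7.3 | Analysis made up of those who completed |

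No reading of 7.3 as a completers-only set agrees with the other two.

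**2. The plan's own figures.** Section 7.1 requires 8 patients and allows for about 20% withdrawal: 8 / (1 − 0.20) = 10 enrolled. Conversely, 0.20 × 10 = 2 withdrawals and 10 − 2 = 8 completers.

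**3. Illustration.** Let t be the number of the 2 withdrawals that are due to toxicity. The documents give no value, so t runs over 0, 1 and 2. It is assumed that those who withdraw are non-completers and that no completer stops for toxicity. Not tolerated here means stopped for toxicity, which is a simplification, because the plan's endpoint is a reaction grade. Intervals are exact (Clopper-Pearson) 95%. When the count is 0 the lower limit is 0 and the upper limit is 1 − 0.025^(1/n):

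- n = 8: 1 − 0.025^(1/8) = 1 − 0.631 = 36.9%
- n = 10: 1 − 0.025^(1/10) = 1 − 0.692 = 30.8%

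| t | All treated (n = 10) | Completers (n = 8) |
|---|---|---|
| 0 | 0/10 = 0% (0 to 30.8%) | 0/8 = 0% (0 to 36.9%) |
| 1 | 1/10 = 10% (0.3 to 44.5%) | 0/8 = 0% (0 to 36.9%) |
| 2 | 2/10 = 20% (2.5 to 55.6%) | 0/8 = 0% (0 to 36.9%) |

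The completers' result is 0/8 in every row, whatever the number of toxicity withdrawals. If instead a patient stops the drug for toxicity, attends all follow-up and is counted as a completer, that patient stays in and the difference disappears.

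**4. Visit 2.** The schedule marks four site evaluations, while Sections 2 and 3.4 list three. Section 6.1 says "the subject will be instructed to apply Imiquimod 5% daily Monday to Friday the week prior to the scheduled excision date", which is 5 of 5 × 6 = 30 planned doses (17%). If the last pre-excision dose is on a Friday and excision is on a weekday of the following week, Visit 2 falls 3 to 7 days after that dose. The 2-week rating falls 17 to 21 days after it (3 + 14 to 7 + 14), with 10 further doses planned in between. The later grade therefore cannot stand in for one at Visit 2.

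**The case against.** **Section 7.3 may not exclude anyone.** It says who is included and does not say that others are left out. Completion is undefined, and stopping the drug under 4.4.1 is not the same as leaving the trial. This stands as a limit: a reader might infer that every patient who stops for toxicity will be dropped, and the documents do not support that. They permit it, and they contradict themselves on it, which is enough to need correcting.

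**Toxicity would still be recorded.** Section 8.2 requires that "At each contact with the subject, the investigator must seek information on adverse events by specific questioning and, as appropriate, by examination", and 4.4.2 adds a site visit after withdrawal. So it would be wrong to infer that these reactions go unseen. The weakness lies in which patients enter the tolerability summary, and the data needed to correct it are already being collected.

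**Visit 2 is already planned.** A reader might infer that the pre-excision week is never assessed. The schedule says otherwise: one row label covers all four visits, the protocol has only one reaction scale, and nothing bars reporting a Visit 2 grade. What is left is aligning the text.

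**Two further inferences fail.** One is that patients reacting in the first week fall outside the dose-adjustment rule because Visit 2 is not named for it. Section 5.2 applies the rule at unscheduled toxicity visits, and Section 6.4 says: "If treatment of the lesion with Imiquimod is stopped because of local toxicity, this will prompt an unscheduled clinic visit". No patient who would be missed has been shown. The other is that a Visit 2 grade would serve as each patient's untreated reference. It follows five doses and concerns a keloid that may already itch or hurt (Section 4.1), and no reaction evaluation is scheduled at Visit 1.

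**Conclusion.** Wrong as written: Section 7.3 conflicts with Sections 4.3 and 4.4.1. If it is followed, the tolerability result can lose the patients who left because of toxicity, and the error then makes the drug look better tolerated than it was.

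On the stated assumptions the understatement is 0, 10 or 20 percentage points for 0, 1 or 2 toxicity withdrawals, and the intervals overlap throughout. It is zero if those who stop are kept as completers. These figures show the mechanism and do not predict a result, since the documents give no toxicity rate.

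Importance is low to moderate: the study is a 10-patient pilot, tolerability is reported descriptively, and adverse events are sought at every contact. The Visit 2 mismatch is a minor clarification and does not affect the figures above.

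**What to change.** **Main change.** Reword Section 7.3 so that safety and tolerability are summarised in all patients who applied at least one dose of imiquimod. Report stops for toxicity as not tolerated, alongside the Section 3.4 grades. State that data collected before withdrawal are analysed, so that 7.3 agrees with 4.3 and 4.4.1.

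**Minor clarification.** In Sections 2, 3.4 and 6.2, state that the local site reaction at Visit 2 is graded before excision on the Section 3.4 scale and reported separately from the later grades. Note there that it follows five doses and is not a drug-free baseline.

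**Cost.** A short wording amendment to four sections. The Visit 2 evaluation and the visit after withdrawal are already in the protocol, so no visit, procedure or patient is added and the sample size is unchanged.

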4.1 Inclusion Criteria

1. Age \geq 18
2. Men and women who present clinically with keloids requesting excision
3. Any number of keloids
4. Keloid no larger than 5cm in diameter at the base
5. Clinical findings consistent with keloid formation, including: a scar that does not spontaneously regress, extends beyond borders of normal tissue, may be pruritic, may be painful.
6. Location of keloid in low-risk areas – areas other than above the neck, hands, feet, or groin
7. Able and willing to give informed consent

4.2 Exclusion Criteria

1. Age < 18
2. Hypersensitivity to Imiquimod or to any of the excipients (methylhydroxybenzoate, propylhydroxybenzoate, cetyl alcohol, and stearyl alcohol)
3. Involvement in a trial of another experimental intervention within 30 days
4. Life threatening disease
5. Use of immunosuppressive medications such as oral corticosteroids
6. Bleeding disorders
7. Not available for follow-up for 10 weeks
8. Pregnant, intention to become pregnant during treatment phase of trial, or breastfeeding

4.3 Subject Recruitment and Screening

Patients will be recruited through the routine work of the Dermatology departments at the Hospital of the University of Pennsylvania. Recruitment and consent will be obtained by the principle investigator or another Dermatology physician as delegated by the investigator seeing the patient in the outpatient clinic. Patients seen in the outpatient clinic with clinical representation of keloids will be approached by the

CONFIDENTIAL

Dermatology attending as part of clinical evaluation, and written, informed consent will be obtained from the patient prior to any research related procedures are conducted.

It will be explained to the potential participant that entry into the trial is entirely voluntary and that their treatment and care will not be affected by their decision. Should any Penn affiliates be approached, that their decision of whether to participate will not impact their standing with the institution. It will also be explained that they can withdraw at any time. In the event of their withdrawal it will be explained that their data collected so far will be retained and used as part of the study analysis.

4.4 Early Withdrawal of Subjects

4.4.1 When and How to Withdraw Subjects

The participant will stop Imiquimod treatment early for the following reasons:

- New clinical/diagnostic information (e.g. pathology report) suggests a diagnosis other than keloid
- Intolerable local or systemic toxicity from Imiquimod
- Clinical evidence of keloid recurrence. These participants will progress to intralesional steroid injections or excision as per standard of care.
- Any participant who becomes pregnant during the study
- Withdrawal of consent

Subjects who withdraw consent will be withdrawn from the trial. The subjects will be made aware that this will not affect their standard of care. Subjects will be made aware (via the information sheet and consent form) that should they withdraw the data collected will be retained and used as part of the study analysis.

4.4.2 Data Collection and Follow-up for Withdrawn Subjects

Protected Health Information to be collected include names and medical record numbers. Additional information that is to be collected from patient's electronic medical record are:

- Race/ethnicity/gender
- And all elements of dates for dates that are directly related to the patient
- Current medications
- Symptoms related to treatment
- Physical examination
- Treatment and response
- Unidentifiable photodocumentation of lesions

Patients who choose to withdraw from the trial will be asked for permission for phone follow-up 12 weeks after excision date.

Patients who are withdrawn from the study for any reason but have initiated at least 1 imiquimod treatment will be seen in the outpatient clinic for one additional follow-up visit after their withdrawal date to observe the application site.

This information will be associated with a study ID. A master list with PHI and study IDs will be maintained by personal investigators in a secure location. Access will be given to only study personnel as needed. Data sets will only include assigned study IDs. Data will be backed up as a password protected file on a Penn Medicine secure server. Links to identifiers will be destroyed after the study is completed.

5 Study Drug

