6.5 Phone follow-up (Encounter 6)

Patient will be contacted by phone 12 weeks after surgical excision of keloid (7 weeks after completing Imiquimod therapy). Patient will be asked about recurrence of keloid at excision site and any residual local site symptoms from Imiquimod therapy.

CONFIDENTIAL

7 Statistical Plan

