7.1 Sample Size Determination

In this open-label, single-arm pilot study, 10 patients will be enrolled.

The sample size calculation was based on a historical recurrence rate of 70% at 8 week follow-up after excision alone and an expected 25% recurrence rate with Imiquimod treatment. Using 80 % power and $\alpha = 5\%$, the estimated sample size required is 8. Allowing for a withdrawal rate of approximately 20 %, 10 subjects will have to be enrolled.

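### For withdrawn patients, Section 4.4.2 does not assure an examined recurrence status at 8 weeks, although it already plans a clinic visit for those who started imiquimod

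*Combined protocol and SAP*

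**What the plan says.** Section 4.4.2 provides two contacts after withdrawal.

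- **Clinic.** Patients withdrawn for whatever reason, once they have started imiquimod, "will be seen in the outpatient clinic for one additional follow-up visit after their withdrawal date to observe the application site". No time is given and no assessment is named beyond looking at the site.
- **Phone.** "Patients who choose to withdraw from the trial will be asked for permission for phone follow-up 12 weeks after excision date". Section 6.5 describes the study's 12-week call: "Patient will be asked about recurrence of keloid at excision site and any residual local site symptoms from Imiquimod therapy".

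For patients who stay in the study, Section 2 sets the primary assessment: "Subjects will be evaluated by a consultant dermatologist at 2, 4, and 8 weeks following excision", with a 12-week phone contact as well. Sections 6.3 and 6.4 ask the investigator at Visits 3, 4 and 5 for a recurrence evaluation and a local reaction grade on the Section 3.4 scale.

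Section 7.1 fixes the time point and the expected loss: "The sample size calculation was based on a historical recurrence rate of 70% at 8 week follow-up after excision alone", against "an expected 25% recurrence rate with Imiquimod treatment"; then "the estimated sample size required is 8"; then "Allowing for a withdrawal rate of approximately 20 %, 10 subjects will have to be enrolled".

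Sections 4.3 and 4.4.1 say that data collected before withdrawal are kept and used in the analysis. Section 7.3 restricts the analysis to subjects who completed the protocol.

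**The concern.** A withdrawn patient who has had the excision may return to clinic and have the excised site looked at, with no instruction to record whether the keloid has come back. With no date set, the visit may also fall well before 8 weeks. The remaining source, the phone call, is optional and self-reported, and it comes four weeks after the time point used for the sample size.

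Patients who leave because of a reaction or dissatisfaction may differ in exposure and outcome from those who stay. With 10 patients, each unknown outcome can move the recurrence rate by 10 percentage points. An examination that was never made cannot be recovered at the analysis stage, so the collection rule has to be settled beforehand.

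**Working it through.** **1. Is recurrence evaluation part of observing the site?**

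- The schedule in Section 6 has separate rows for local site reaction and for recurrence. Visit 2 is marked only for the first; Visits 3 to 5 are marked for both; the phone encounter is marked for recurrence.
- Sections 6.3 and 6.4 also list the two separately.
- Section 5.2 defines the treated area as the lesion plus a 1 cm margin, so after surgery the application site includes the endpoint site. The clinician is looking at the right place, but the protocol does not ask for the endpoint to be recorded.

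**2. Timing.** Excision is at week 2, Visit 5 at week 10 and the call at week 14. So Visit 5 is 10 − 2 = 8 weeks after excision, the call is 14 − 2 = 12 weeks after, and the call comes 12 − 8 = 4 weeks after the Section 7.1 time point.

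**3. The plan's own figures.** Inputs from Section 7.1: p0 = 0.70, p1 = 0.25, alpha 5%, power 80%, withdrawal about 20%. The documents do not say whether alpha is one- or two-sided; two-sided is assumed here. One-sample normal approximation:

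n = [1.960·√(0.70·0.30) + 0.842·√(0.25·0.75)]² / (0.70 − 0.25)² = 7.87, rounded up to 8.

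Enrolled: 8 / (1 − 0.20) = 10. Both figures reproduce. The allowance is 0.20 × 10 = 2 patients.

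**4. Worst-case effect of two unknown outcomes.** Assume that the 8 others recur at the expected rate: 0.25 × 8 = 2. Section 7.2 names no interval method; Clopper-Pearson is used here, with lower limit the 2.5% quantile of Beta(x, n − x + 1) and upper limit the 97.5% quantile of Beta(x + 1, n − x).

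| Case | Recurrences | Rate | 95% interval |
|---|---|---|---|
| The 8 with known outcome | 2/8 | 25% | 3.2% to 65.1% |
| Neither unknown patient recurs | 2/10 | 20% | 2.5% to 55.6% |
| One recurs | 3/10 | 30% | 6.7% to 65.2% |
| Both recur | 4/10 | 40% | 12.2% to 73.8% |

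The range is 40% − 20% = 20 percentage points. Only when both recur does the upper limit pass the 70% historical rate.

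**5. How the range shrinks.** With k unknown outcomes among 10, its width is k/10: 20 points for k = 2, 10 points for k = 1, none for k = 0. The documents do not say how many of the two would lack a known outcome.

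**The case against.** A reader might infer that recurrence is never examined in withdrawn patients and that the primary endpoint is lost for the 20% expected to leave. The documents do not support that, for five reasons.

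- Patients who leave after Visit 3 or later already have one or more examined assessments. This stands, though a clear site at 2 or 4 weeks does not give the status at 8 weeks.
- Recurrence is itself a listed reason for stopping in Section 4.4.1, and for those patients the endpoint is known. This stands.
- The 12-week call is one of the recurrence assessments named in the primary objective, so it cannot be dismissed. This stands, within its limits: it needs permission, is self-reported, and is offered only to patients who choose to withdraw, a narrower group than the clinic visit covers.
- The data list in 4.4.2 includes physical examination, treatment response and lesion photographs. These might capture recurrence, but the list gives no timing and no recurrence assessment.
- Section 4.4.1 lists reasons to stop imiquimod and then says separately that those who withdraw consent leave the trial. A patient who stops for toxicity may therefore be off drug but still on study, keeping Visits 3 to 5. Section 6.4 also prompts an unscheduled visit when treatment stops for local toxicity. The section heading points the other way, so the text leaves this open. If only consent withdrawals are affected, the group is smaller and perhaps less willing to return.

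It can also be said that the interval from 8 patients is already wide, so two unknown outcomes add only modestly to the uncertainty of a descriptive pilot. That is fair as to size. It is no reason to leave the endpoint unrecorded at a visit that is taking place anyway.

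**Conclusion.** The point holds in a limited form. The visit after withdrawal has no set time and does not call for the recurrence evaluation or the reaction grade, and the only other planned recurrence follow-up is an optional phone report. An examined 8-week status is not assured for withdrawn patients; that is weaker than saying it will be absent.

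The 20% to 40% range is a worst case. It assumes that both patients in the planning allowance withdraw after excision, that neither has a usable earlier examination or phone answer, and that 2 of the other 8 recur. The 20% is a planning figure and does not forecast missing outcomes. Patients who leave before excision have no recurrence endpoint and are outside the point.

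Better collection alone would not be enough. Section 7.3 as written would exclude these patients even when their status is known, contrary to Sections 4.3 and 4.4.1.

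**What to change.** 1. **Section 4.4.2.** For patients who have had the excision, record the recurrence evaluation and the Section 3.4 reaction grade at the post-withdrawal visit already planned. Leave the timing of that visit for safety as it is.
2. **Section 4.4.2.** Ask patients who agree to keep the 8-week Visit 5 examination already on the schedule.
3. **Section 4.4.1.** State whether patients who only stop imiquimod remain on study for Visits 3 to 5.
4. **Section 7.3.** Reconcile it with Sections 4.3 and 4.4.1, so that the outcomes of withdrawn patients enter the recurrence rate. Show any outcome that is still unknown with best- and worst-case bounds, as in the table above.

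The cost is a few sentences and use of the existing Visit 5 assessments. On the plan's own allowance, about two patients may be asked for one more scheduled visit. Some may decline, so the range may narrow without closing.
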